6.3 Modification of Study Intervention/Investigational Product for a Subject

Any dosage adjustment, including the reason for and dates of adjustment, will be documented in the CRF for each subject requiring this manipulation. The PIs or licensed physician Sub-Investigator may reduce the dosage of study drug or discontinue the study drug in its entirety for AEs thought to be related to the study drug or for other reason during the trial (the reason for, and dates of suspension or dose reduction must be documented). If the AE is mild or moderate, the dosage may be reduced until the event improves. The PIs may then choose to resume the higher dosage or maintain the subject at a reduced dosage. The option to continue with administration by IV only or inhalation only is allowable.

If the event is serious or life threatening, and deemed to be definitely drug related, the study drug will be discontinued immediately. Study subjects must remain off the study drug permanently. Subjects may not resume study drug. All AEs will be followed to resolution.

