9.1 Definitions of AEs, Suspected Adverse Drug Reactions & SAEs

9.1.1 Adverse Event and Suspected Adverse Drug Reactions

An adverse event (AE) is any unfavorable and unintended sign (including a clinically significant abnormal laboratory finding, for example), symptom, or disease temporally associated with the study, use of a drug product or device whether or not considered related to the drug product or device.

Adverse drug reactions (ADR) are all noxious and unintended responses to a medicinal product related to any dose. The phrase “responses to a medicinal product” means that a causal relationship between a medicinal product and an adverse event is at least a reasonable possibility, i.e., the relationship cannot be ruled out. Therefore, a subset of AEs can be classified as suspected ADRs, if there is a causal relationship to the medicinal product.

Examples of AEs include: new conditions, worsening of pre-existing conditions, clinically significant abnormal physical examination signs (i.e. skin rash, peripheral edema, etc), or clinically significant abnormal test results (i.e. lab values or vital signs), with the exception of outcome measure results, which are not being recorded as AEs in this trial (they are being collected, but analyzed separately). Stable chronic conditions (i.e., diabetes, arthritis) that are present prior to the start of the study and do not worsen during the trial are NOT considered AEs. Chronic conditions that occur more frequently (for intermittent conditions) or with greater severity, would be considered as worsened and therefore would be recorded as AEs.

AEs are generally detected in two ways:

Clinical → symptoms reported by the subject or signs detected on examination.

Ancillary Tests → abnormalities of vital signs, laboratory tests, and other diagnostic procedures (other than the outcome measures, the results of which are not being captured as AEs).

For the purposes of this study, symptoms of progression/worsening of ALS, including ‘normal’ progression, will be recorded as AEs.

The following measures of disease progression will not be recorded as AEs even if they worsen (they are being recorded and analyzed separately): vital capacity results and ALSFRS-R results.

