9.2.2 Relatedness of Adverse Event to Investigational Product

The relationship of the AE to the investigational product should be specified by the PIs, using the following definitions:

RNS60 in ALS

V 4.0

1/29/2016

1. Not Related: Concomitant illness, accident or event with no reasonable association with treatment.
2. Unlikely: The reaction has little or no temporal sequence from administration of the investigational product, and/or a more likely alternative etiology exists.
3. Possibly Related: The reaction follows a reasonably temporal sequence from administration of the investigational product and follows a known response pattern to the suspected investigational product; the reaction could have been produced by the investigational product or could have been produced by the subject's clinical state or by other modes of therapy administered to the subject. (Suspected ADR)
4. Probably Related: The reaction follows a reasonably temporal sequence from administration of investigational product; is confirmed by discontinuation of the investigational product or by re-challenge; and cannot be reasonably explained by the known characteristics of the subject's clinical state. (Suspected ADR)
5. Definitely Related: The reaction follows a reasonable temporal sequence from administration of investigational product; that follows a known or expected response pattern to the investigational product; and that is confirmed by improvement on stopping or reducing the dosage of the investigational product, and reappearance of the reaction on repeated exposure. (Suspected ADR)

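### The mandatory permanent stop in 6.3 needs a Definitely Related grade, which 9.2.2 gives only after recurrence, so it cannot act on a serious reaction with no earlier episode in that subject

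*Combined protocol and SAP*

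**What the plan says.** Section 6.3 treats drug-related adverse events in two ways. The general rule is permissive: a principal investigator or licensed physician sub-investigator "may reduce the dosage of study drug or discontinue the study drug in its entirety". After a mild or moderate event the dose may be lowered and later raised again. The mandatory rule is narrower: "If the event is serious or life threatening, and deemed to be definitely drug related, the study drug will be discontinued immediately". That stop is permanent.

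Section 9.2.2 defines five relatedness grades and tells the investigators to use them. Three are labelled as suspected adverse drug reactions:

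- Possibly Related requires, among other things, that the reaction "follows a known response pattern to the suspected investigational product".
- Probably Related requires that it "is confirmed by discontinuation of the investigational product or by re-challenge" and that it "cannot be reasonably explained by the known characteristics of the" subject's clinical state.
- Definitely Related requires a known or expected pattern and that the reaction is "confirmed by improvement on stopping or reducing the dosage of the investigational product, and reappearance of the reaction on repeated exposure".

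Section 9.1.1 sets a lower threshold for an adverse drug reaction: a causal link that "is at least a reasonable possibility, i.e., the relationship cannot be ruled out".

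Section 5.3 separately requires that a subject be discontinued in either of two situations: an adverse event or other condition makes continuing contrary to the subject's best interest, or the subject meets any exclusion criterion, including one that develops during the study.

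**The concern.** A stop that is meant to be immediate and final is tied to a grade that already presupposes stopping or reducing the drug, exposing the subject again, and seeing the reaction return. For a serious reaction that arrives without warning, the rule is not available when it is wanted. A serious event graded Probably Related is a suspected drug reaction on the protocol's own label, yet no rule based on that grade prevents further dosing.

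Safety is the first primary outcome in 3.2, and the dosing schedule leaves little slack. Drug is scheduled every day, mostly by nebulizer at home (6.1.2). Unless someone decides to hold it, the next dose falls due the next day.

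**Working it through.** There is no stated figure to reproduce. The check sets the trigger in 6.3 against the definitions in 9.2.2.

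**Step 1: the trigger.** Mandatory permanent stop = (serious or life threatening) AND (definitely drug related).

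**Step 2: the grades that count as suspected drug reactions.**

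| Grade in 9.2.2 | Confirmation required | Fewest episodes in one subject | Mandatory stop in 6.3 if serious |
|---|---|---|---|
| Possibly | none, but a known response pattern | 1 | no |
| Probably | discontinuation or re-challenge | 1 | no |
| Definitely | improvement on stopping or reducing, and recurrence on re-exposure | 2 | yes |

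The mandatory stop covers 1 of the 3 grades.

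**Step 3: when the stop can act.** Definitely Related = first episode + improvement + recurrence, so at least 2 episodes of the same reaction. The stop can still act on a first *serious* episode if milder episodes of that reaction had already improved and come back, for example after the dose reduction and return to the higher dose that 6.3 allows. Without such a history it cannot act.

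**Step 4: what else would stop the drug.**

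- 6.3, permissive: any event thought to be related, at the investigator's discretion.
- 5.3, best interest: mandatory once the judgement is made, with no link to seriousness or relatedness grade.
- 5.3, newly met exclusion criterion: mandatory, on a first occurrence and whatever the relatedness. Through 5.2.2 this covers AST or ALT above 3 times the upper limit of normal and creatinine above 1.5 times, both objective. It also covers a clinically significant unstable condition other than ALS that would pose a risk, which needs clinical judgement.

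So a first serious reaction that shows as one of those laboratory abnormalities is already caught. Most other kinds depend on a judgement in the individual case.

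**Step 5: exposure.** 1 infusion + 6 home inhalations per week = dosing on 7 of 7 days.

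**Step 6: effect of the remedy proposed below.** The hold can act at 1 episode. The permanent stop can also act at 1 episode, but only if the event improves off drug, because Probably Related must be confirmed. A reaction that does not reverse may never reach that grade, so it needs a restart rule of its own.

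**Step 7: price in the tolerability outcome.** Tolerability is completion of the 24-week treatment period (3.2). One further non-completer lowers the observed proportion by 1/18 = 0.0556, or 5.6 percentage points, with the 18 subjects of 3.1 and 4.1. With the 15 of 5.1 and 6.7 it is 1/15 = 0.0667, or 6.7 points.

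**The case against.** The best reply is that subjects are already protected. 5.3 is mandatory, not advisory, and its exclusion-criterion limb acts on a first event without any relatedness grade. This stands, and it narrows the point considerably. A reader might infer from 6.3 and 9.2.2 that nothing compels a stop after a first serious reaction; the documents do not support that.

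A second reply is that 6.3 does not cite 9.2.2, and that an order to stop immediately is hard to read as waiting for recurrence; the natural meaning is that the investigator is convinced. That is a fair account of the probable intention. But 9.2.2 directs the investigators to grade by its definitions, is the only scale in the readable text, and has a grade of that name. An investigator who follows the protocol closely will arrive at the restrictive reading.

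A third reply is that every route, the remedy included, uses investigator judgement. True. The difference is the default: under 6.3 dosing continues unless someone decides to stop, whereas under a hold it stops unless someone decides to restart.

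A reader might also infer that the protocol requires deliberate re-challenge after a serious event. It does not. No section calls for it, and recurrence could equally come from continued scheduled dosing.

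**Conclusion.** The point holds in a limited form. The only relatedness-based mandatory stop cannot act on a serious reaction with no earlier episode in that subject, and no grade-based rule bars re-dosing after a serious event graded Probably Related. The practical gap is confined to serious reactions outside the objective laboratory criteria.

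The size can be given only structurally: two episodes needed where one should suffice. With no rate of serious drug reactions in the documents, no frequency of harm can be estimated. No estimate, analysis or power figure is affected. This is a rule of safety conduct, not an analysis choice, and correcting it is a cheap improvement.

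The conclusion assumes that the wording in 6.3 refers to the grade of the same name in 9.2.2, and that no redacted text supplies another rule.

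**What to change.** Replace the trigger sentence in 6.3 with a rule to this effect:

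- Study drug is held for any serious or life-threatening event for which a causal relationship cannot be ruled out (9.1.1).
- Discontinuation is permanent if the event is graded Probably or Definitely Related.
- No subject is re-exposed to confirm the grade of a serious event.
- For any other held event, including one that does not improve off drug, drug restarts only on a documented decision by a principal investigator that the drug is not the likely cause and that continuing is in the subject's best interest.

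Base the hold on the 9.1.1 threshold, not on the Possibly Related grade, because a new kind of reaction may have no known response pattern and so fail that grade.

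The change is wording in one section and needs no extra visits or staff. It does have a price. "For the purposes of this study, symptoms of progression/worsening of ALS" are recorded as adverse events, so some subjects will miss doses during a hold for an event that proves to be ALS. A few more may stop before 24 weeks, each at the tolerability cost in Step 7. Setting the permanent stop at Probably limits this, since that grade excludes events that the subject's clinical state reasonably explains.

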6.3.1. Dosage Discontinuation

Reasons for discontinuation of study medication may include an AE, PI recommendation, protocol deviation, loss-to-follow-up, patient request, or patient death.

Study subjects who discontinue study drug prematurely (early termination from study) will be encouraged to return for a Final Safety Visit and participate in a Follow-Up Telephone Call 28 days (+ 5 days) after the last dose of study drug.

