RNS60 infusion		X	X	X	X	X			
RNS60 Dispensing (for inhalation)		X	X (week 7)		X (week 15)				
RNS60 Accountability			X	X	X	X			X
AE review ⁸	X	X	X	X	X	X	X		X
Concomitant Meds	X	X	X	X	X	X	X		X
Collection of blood biomarkers		X		X		X			X

¹ Screening procedures must be completed within 6 weeks prior to Baseline Visit.

RNS60 in ALS

V6.0

5/5/2016

² Follow-up will continue every 3 months up to 2 years to collect data on SVC, ALSFRS-R, and survival status. This information may be obtained via chart review and patient contact.

³ Follow-up phone call to occur 28 +5 days after the last dose of study drug if a subject discontinues from the study prematurely.

⁴ Safety labs include Hematology (CBC with differential), Complete Chemistry Panel, Liver Function Tests, Urinalysis, Urine pregnancy test (WOCBP).

⁵ Vital signs include systolic and diastolic pressure in mmHg, respiratory rate/minute, heart rate/minute, temperature and weight. Height measured at Screening Visit only.

⁶ The Penn Upper Motor Neuron-Burden (UMN-B) includes testing of reflexes, the CNS Lability Scale (CNS-LS) and the Ashworth Spasticity Scale.

⁷ If time permits, ATLIS will be performed at the screening visit.

⁸ Adverse events that occur AFTER signing the informed consent form will be recorded.

^{*Off}treatment [¹¹C]PBR28-PET will be performed one time only between the Screening and Baseline visit. ALSFRS-R and SVC will be repeated on the day of the scan.

^{**On}treatment [¹¹C]PBR28-PET will be performed one time only between the Week 18 and Week 23 visits. ALSFRS-R and SVC will be assessed the day of the scan ONLY.

[†]For subjects in the “Imaging group” only.

SCHEDULE OF ACTIVITES – OPTIONAL EXTENSION PHASE

	Weekly visits Week 24 through Week 34	Week 35	Weekly visits Week 36 through Week 46	Week 47	Week 52 Phone Call	Follow Up Chart Review / Phone Call ²	Final Safety Visit (for early study drug discontinuation only) ¹
Visit Window	Day 168 ± 3	Day 245 ± 3	Day 252 ± 3	Day 329 ± 3	Day 364 ± 3	Every 3 months	
12-lead ECG		X		X			X
Safety Labs ³		X		X			X
Vital Signs / Weight ⁴	X	X	X	X			X
Neurological exam				X			X
Physical exam				X			X
ALSFRS-R		X		X	X	X	X
Slow Vital Capacity		X		X		X	X
C-SSRS		X		X			X
RNS60 infusion	X	X	X	X			
RNS60 Dispensing (for inhalation)	X (week 30)		X (week 38)				
RNS60 Accountability	X	X	X	X			X
AE review ³	X	X	X	X	X		X
Concomitant Meds	X	X	X	X	X		X

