5.3.1 Handling of Withdrawals

A subject may choose to discontinue participation in the study at any time. Subjects who permanently discontinue study drug should complete early study drug termination procedures per protocol. The subject should then return any unused study drug and will be asked to return to the study site for a final safety visit. At that visit, the subject will be asked to have a final telephone call 28 days (+ 5 days) after taking their last dose of study drug.

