7.9 Final Safety Visit

Subjects who withdraw consent will be asked to come in for a Final Safety Visit as soon as possible, and will be asked to have a final Follow-Up Telephone Call (+ 5 days, but no earlier than 28 days, after subject's last dose of study drug) to assess for adverse events.

The following will be performed at the Final Safety Visit:

- Measure vital signs
- Perform ECG
- Perform neurological exam
- Perform physical exam
- Collect blood samples for safety labs
- Collect blood for biomarkers
- Administer ALSFRS-R questionnaire
- Perform U. Penn upper motor Neuron Burden (UMNB)
- Perform Pulmonary Function Tests
- Measure strength (ATLIS)
- Columbia Suicide Severity Rating Scale (C-SSRS) – Since last visit
- Review and document concomitant medications and therapies
- Assess and document AEs
- Check study drug compliance
- Perform study drug accountability and collect all unused study drug and empty containers and nebulizers

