7.10 Follow-up

After the Week 28 Follow-up Telephone Interview, subjects may be contacted every three months for up to two years, or until consent is withdrawn, in order to obtain vital status and clinical information including the ALSFRS-R. Additionally, two years of post-study access to subjects' medical records will be requested to allow for review in combination with study data in order to investigate any correlation between imaging data collected during this study and subjects' clinical outcomes.

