8.1.6 ALSFRS-R

The ALSFRS-R is a quickly administered (5 minutes) ordinal rating scale (ratings 0 to 4) used to determine subjects' assessment of their capability and independence in 12 functional activities. All 12 activities are relevant in ALS. Initial validity was established by documenting that in ALS patients, change in ALSFRS-R scores correlated with change in strength over time, was closely associated with quality of life measures, and predicted survival. The test-retest reliability is greater than 0.88 for all test items. The advantages of the ALSFRS-R are that the categories are relevant to ALS, it is a sensitive and reliable tool for assessing activities of daily living function in those with ALS, and it is quickly administered. With appropriate training the ALSFRS-R can be administered with high inter-rater reliability and test-retest reliability. The ALSFRS-R can be administered by phone with good inter-rater and test-retest reliability. The equivalency of phone versus in-person testing, and the equivalency of study subject versus caregiver responses have also recently been established. Therefore, if necessary, the ALSFRS-R may be given to the study subject over the phone.

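### Stopping study drug is treated as leaving the study, so a subject who stops has no assessment at the Week 11 or Week 23 dates still to come

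*Combined protocol and SAP*

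**What the plan says.** Section 6.3.1 describes the group as "Study subjects who discontinue study drug prematurely (early termination from study", and asks them, without obligation, to attend a Final Safety Visit. The parenthesis makes the two events one. Footnote 3 of the core Schedule of Activities does the same: it belongs to a column reserved for early discontinuation of study drug, yet it applies "if a subject discontinues from the study prematurely". Section 5.3.1 adds: "Subjects who permanently discontinue study drug should complete early study drug termination procedures per protocol". It then describes return of drug, a final safety visit and a call about 28 days after the last dose. No section asks a subject who is off drug to attend Week 11 or Week 23.

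Some outcome data are planned after stopping. Section 7.9 lists "Administer ALSFRS-R questionnaire" at the Final Safety Visit, together with pulmonary function, ATLIS, upper motor neuron burden and blood biomarkers. Subjects "will be asked to come in for a Final Safety Visit as soon as possible", so the visit is tied to the stop and not to the outcome schedule.

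The later contacts are worded in different ways. Section 7.10 is permissive: "After the Week 28 Follow-up Telephone Interview, subjects may be contacted every three months for up to two years". The Protocol Summary and footnote 2 of the schedule state the 3-monthly contacts as definite.

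Section 3.2 lists ALSFRS-R, SVC, ATLIS and blood biomarkers among the primary outcome measures. Section 6.7 gives no analysis set, estimator or missing-data rule for change in the clinical outcomes.

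**The concern.** Stopping drug and leaving the study are different events. Someone who stops an infusion or a nebulizer can often still answer a questionnaire. When the plan merges the two, outcome collection on the scheduled dates ends with the drug.

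This matters more than usual here for two reasons. The trial has a single open-label arm, so there is no control group in which the same loss would partly cancel. The analysis is also unspecified, so nothing at that stage makes up for values that were never collected. If subjects who stop are declining faster, the reported 24-week change in function, breathing and strength would look milder than it was in the people treated. The documents do not say that those who stop decline faster; it is an assumption.

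**Working it through.** **1. What a subject who stops drug would contribute**

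| Contact | Content | Limitation |
|---|---|---|
| Week 11 visit | All non-imaging outcomes | Present only if the subject stopped later |
| Week 23 visit | All non-imaging outcomes | Not provided for off drug |
| Final Safety Visit (6.3.1, 7.9) | ALSFRS-R, SVC, ATLIS, biomarkers | Voluntary; soon after stopping. 7.9 introduces it for withdrawal of consent, the schedule for drug discontinuation |
| Call about 28 days after last dose | AEs in 7.9; ALSFRS-R as well in 4.3 | Sections differ; tied to last dose |
| Week 28 call (Protocol Summary) | ALSFRS-R, for each subject | Unclear whether it applies after an early stop; Day 196 against Day 161 for Week 23, 35 days later |
| 3-monthly contacts | ALSFRS-R and vital status; SVC in the schedule | After the Week 28 call (7.10) or after trial completion (Protocol Summary); no ATLIS |

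No row guarantees a value at Week 23.

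**2. How many subjects**

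The plan has no dropout forecast. The nearest figures are the tolerability benchmarks in section 6.7, and these reproduce: with 15 subjects, the binomial probability of 10 or more tolerating is 0.852 at a true rate of 75% and 0.034 at 40%, against the stated 85% and 3%. Taken as a rough guide, a 75% rate means 25% stop: 0.25 × 15 = 3.75, or 0.25 × 18 = 4.5. Ten of 15 means 33% stop: 5 of 15, or 6 of 18. That is about 4 to 6 subjects.

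**3. Illustrative size**

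Let q be the fraction who stop and r their rate of decline relative to completers, with completers' decline set at 1. The documents give no value for r; 1.5 to 2 is assumed. Mean decline in all treated subjects is (1 − q) + qr.

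- Completers only: understatement = 1 − 1/((1 − q) + qr).
- Last value carried forward, assuming linear decline and a stop halfway on average: understatement = (qr/2)/((1 − q) + qr).

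| q | r | True mean | Completers only | Last value |
|---|---|---|---|---|
| 0.25 | 1.5 | 1.125 | 11% | 17% |
| 0.25 | 2 | 1.25 | 20% | 20% |
| 0.333 | 1.5 | 1.167 | 14% | 21% |
| 0.333 | 2 | 1.333 | 25% | 25% |

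Treating the Final Safety Visit value as if it were Week 23 is therefore no better, under these assumptions, than leaving those subjects out. Using it at its actual date, in a method that models decline over time, could recover much of the gap. The plan specifies no such method.

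**The case against.** The strongest reply is that the outcomes are not simply lost, and that stands. Every non-imaging outcome is planned at the Final Safety Visit. Anyone who stops after Week 11 already has Week 11 values. Subjects on a reduced dose or on one route remain in the study under section 6.3.

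A reader might also infer that change from baseline will rest on completers only. The documents do not support that: no analysis set is named, and a slope model using early-termination values fits the text equally well. Nor can the 3-monthly contacts be called optional without qualification, because two of the three places that describe them are definite.

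The size is open to challenge as well. The 25–33% comes from a tolerability benchmark and a decision threshold, not from expected dropout. The completers-only formula gives those who stop no information at all. Section 6.3.1 includes death and loss to follow-up among the reasons for stopping, and no phone call recovers those. The phone route covers ALSFRS-R only; SVC and ATLIS need attendance.

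Finally, off-drug biomarker values may not answer a question about the drug's biological effect, so an on-drug biomarker analysis is defensible. This is also a small pilot sized on safety and tolerability, where those who stop are counted directly.

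What the reply does not supply is a value at Week 23, or a rule for using the values that are collected.

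**Conclusion.** The concern holds in a limited form. A stated rule, not just missing detail, leaves listed primary outcomes uncollected at the remaining scheduled dates once drug is stopped. The substitutes are off schedule, voluntary or inconsistently described. A completers-only or last-value estimate is left open but is not prescribed.

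The 11–25% for a completers-only estimate is an upper-end illustration. It rests on 25–33% stopping, a decline 1.5–2 times as fast in those who stop, and no use of their data. The direction of the bias rests on the same unproven assumption about faster decline. The safety and tolerability aims are unaffected; the clinical-outcome estimates are exposed. The change is worth making because it is cheap, not because the trial fails without it.

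**What to change.** - In sections 5.3.1 and 6.3.1, separate stopping drug from leaving the study. This concerns data collection only and does not touch when or why drug is stopped.
- Unless consent is withdrawn, obtain ALSFRS-R by phone at the remaining Week 11 and Week 23 dates. Section 8.1.6 already allows it: "if necessary, the ALSFRS-R may be given to the study subject over the phone". Add SVC and ATLIS if the subject is willing to attend.
- State that 24-week change in ALSFRS-R, SVC and ATLIS is estimated in all treated subjects, using all available values at their actual dates, including the Final Safety Visit. Give an on-drug analysis as a sensitivity analysis. Biomarker analysis may remain on-drug.
- Reconcile the Protocol Summary, the schedule footnotes and sections 4.3, 6.3.1, 7.9 and 7.10 on which contacts apply after drug is stopped and what each collects.

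Cost: one or two calls each for about 4 to 6 subjects, so at most 12 calls at the benchmark rates, plus any voluntary visits. The downside is a small site workload and some off-drug values in the clinical-outcome estimates, which the sensitivity analysis would make visible.
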